#### **12.4.3 Handling of missing values/censoring/discontinuations**

The method of handling missing data for efficacy endpoints will be described for each set of endpoints. For the primary analysis, missing data will not be imputed, but various sensitivity analyses under missing not at random (MNAR) assumptions will be performed. Missing data will not be imputed for safety endpoints. Details of the missing data handling will be specified in the Statistical Analysis Plan (SAP).

#### **12.4.4 Sensitivity and Supportive analyses**

Multiple imputation (MI) techniques applying MNAR approaches will be used to assess the impact of missing values on the interpretation of the results during study. In addition, the baseline observations carried forward (BOCF) method will also be used.

### **12.5 Analysis of secondary endpoints**

#### **12.5.1 Efficacy and/or Pharmacodynamic endpoint(s)**

The secondary efficacy variables (all during the 12-week treatment period) are:

- Proportion of subjects who achieve at least a 50% reduction from baseline in monthly migraine days during the last 4 weeks of the 12-week treatment period.
- Change from baseline in monthly acute headache medication days during the last 4 weeks of the 12-week treatment period
- Change from baseline in migraine-related disability and productivity as measured by modified MIDAS during the last 4 weeks of the 12-week treatment period

The above continuous endpoints (i.e. change from baseline) will be analyzed using a generalized linear mixed effects model similar to the primary endpoint. The dichotomous endpoints will be analyzed by Cochran-Mantel-Haenszel (CMH) test with subjects who are missing monthly migraine day data during the last 4 weeks of the treatment period imputed as non-responders. Nominal 95% confidence intervals and p-values will be reported. Tests of secondary endpoints will be tested at nominal 2-sided significant level 0.05.

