### **10.2.3 Data Monitoring Committee**

This study will include a DMC which will function independently of all other individuals associated with the conduct of this clinical trial, including the site investigators participating in the study.

The DMC will conduct regular unblinded safety reviews of cumulative safety data. In addition, the DMC will assess efficacy and safety data at the pre-defined unblinded interim analysis timepoint (see [Section 12.7](#)).

This unblinded IA will be conducted after 70% (385) of subjects have completed the treatment period (including early withdrawals). Although this unblinded IA will focus on the primary efficacy endpoint, the secondary efficacy endpoints and safety data will also be assessed. The DMC recommendation on whether to stop the trial or not will be based on the evaluation of the totality of efficacy and safety data at the interim cut-off. The study team will not be unblinded unless the study is stopped early for success.

Specific details regarding composition, responsibilities, data monitoring and meeting frequency, and documentation of DMC reports, minutes, and recommendations will be described in a separate charter that is established between the sponsor and the DMC.

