In case of a positive IA read-out with 70% information, the analysis results will be prepared for regulatory submission. Subjects who are ongoing at the cut-off time of the interim analysis will not be included in the unblinded interim analysis. Their data and all data collected beyond the IA cut-off will be analyzed separately.

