2.6.2 Statistical hypothesis, model, and method of analysis

Analysis of secondary efficacy endpoints will utilize the FAS. Subjects will be analyzed according to their randomized treatment group regardless of the actual treatment received during the study.

The above continuous change from baseline efficacy endpoints will be analyzed using a linear mixed effects repeated measures model similar to the primary efficacy variable.

The dichotomous endpoint (Proportion of subjects who achieve at least a 50% reduction from baseline in monthly migraine days in the last 4 weeks of the 12-week treatment period) will be analyzed based on Cochran-Mantel-Haenszel (CMH) test after subjects who have missing monthly migraine day data at the last 4 weeks imputed as non-responders.

The description of the models can be found in [Section 5.4](#)

In all cases, estimates (difference or odds ratio) of treatment group compared to placebo group with associated nominal 95% confidence intervals and nominal two-sided p-values will be provided.

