2.12.2 Unblinded Interim Analysis

An unblinded IA will be conducted after 70% (385) of subjects have completed the DB treatment period (including early withdrawals), to determine whether the study will stop early or continue to the primary analysis (full sample size in DB period). The following data analysis (excluding OLE period) will be included in IA read-out.

- Subject disposition (as defined in [Section 2.3.1](#))
- Demographics and baseline characteristics (as defined in [Section 2.3.2](#))
- Study treatment / Compliance (as defined in [Section 2.4.1](#))
- The primary and sensitive analysis on key efficacy endpoints:
 - The change from baseline in monthly migraine days in the last 4 weeks of the 12-week treatment period (as defined in [Section 2.5](#))
 - Proportion of subjects who achieve at least a 50% reduction from baseline in monthly migraine days in the last 4 weeks of the 12-week treatment period (as defined in [Section 2.6](#))
 - Change from baseline in monthly acute headache medication days during the last 4 weeks of the 12-week treatment period (as defined in [Section 2.6](#))

- Change from baseline in migraine-related disability and productivity as measured by modified MIDAS during the last 4 weeks of the 12-week treatment period (as defined in [Section 2.6](#))
- The primary analysis on key safety endpoints:
 - Adverse events (as defined in [Section 2.7.1](#))
 - Laboratory evaluations - Hematology, Chemistry and Urinalysis (as defined in [Section 2.7.3](#))
 - ECG evaluations (as defined in [Section 2.7.4.1](#))
 - Vital signs (as defined in [Section 2.7.4.2](#))
- Subgroup analysis in Chinese sub-population: repeat the primary analysis for following efficacy endpoints and safety endpoints
 - The change from baseline in monthly migraine days in the last 4 weeks of the 12-week treatment period (as defined in [Section 2.5](#)). Sensitive analyses for primary endpoint will not be conducted for Chinese sub-population.
 - Proportion of subjects who achieve at least a 50% reduction from baseline in monthly migraine days in the last 4 weeks of the 12-week treatment period (as defined in [Section 2.6](#))
 - Change from baseline in monthly acute headache medication days during the last 4 weeks of the 12-week treatment period (as defined in [Section 2.6](#))

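### Three secondary efficacy endpoints are each tested at nominal 0.05 with no order, no adjustment and no dependence on the primary result, so the trial as written cannot support error-controlled secondary claims; a fixed sequence would be a cheap improvement

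*Protocol*

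**What the plan says.** Protocol 12.5.1 introduces the list with "The secondary efficacy variables (all during the 12-week treatment period) are" and gives three bullets: 50% responder rate, monthly acute headache medication days and mMIDAS. It then says "Nominal 95% confidence intervals and p-values will be reported" and "Tests of secondary endpoints will be tested at nominal 2-sided significant level 0.05". The protocol summary carries the same rule.

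SAP 2.6.2 says that estimates "with associated nominal 95% confidence intervals and nominal two-sided p-values will be provided". It does not repeat the 0.05 level and adds no order, condition or adjustment. SAP section 4 records no change to the protocol analyses, so the protocol rule stands.

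No testing sequence can be read from the lists. Protocol Table 2-1 and SAP 2.6.1 start with mMIDAS; Protocol 12.5.1 and SAP 2.12.2 start with the responder rate.

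Alpha spending (Protocol 12.4.2 and 12.7, SAP 2.5.2) is attached to the primary hypothesis only: 0.014 at 70% information and 0.046 at the final analysis.

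The secondaries are also looked at in the unblinded interim. Protocol 10.2.3 says that "the secondary efficacy endpoints and safety data will also be assessed", and SAP 2.12.2 lists all three under "The primary and sensitive analysis on key efficacy endpoints". Protocol 12.7 adds: "In case of a positive IA read-out with 70% information, the analysis results will be prepared for regulatory submission".

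**The concern.** The trial is meant to support registration in China (Protocol 1.2). The protocol does more than report secondary p-values: it names a significance level at which each endpoint is tested. Three tests at 0.05 each do not hold the error of the family at 5%.

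As written, a secondary endpoint could be called significant at 0.05 when the primary had failed. Protocol 12.5.1 does not name a look, so the same 0.05 would by default serve at an interim stop, where the primary needs 0.014. Neither document says that the secondaries are descriptive only or that no confirmatory claim will rest on them. At stake is the standing of the secondary results in the submission.

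**Working it through.** **The plan's own figures.** With information fraction 0.70, the two test statistics for the primary have correlation √0.7. Spending 0.014 at the interim leaves 0.0459 for the final analysis, which matches the stated 0.046. The two rounded levels together give 0.0501. The primary is therefore controlled as stated. The documents give no family-wise figure for the secondaries.

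**Inputs for the secondaries.** k = 3 endpoints, each at two-sided 0.05 (Protocol 12.5.1), so c = 1.96. The correlation ρ between test statistics is not in the documents; 0 to 0.9 is assumed.

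**Independent tests.** 1 − 0.95³ = 1 − 0.857 = 14.3%. For two true nulls, 1 − 0.95² = 9.75%.

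**Equal pairwise correlation ρ.** Chance of at least one rejection = 1 − ∫ φ(u) [Φ((c − √ρ·u)/√(1−ρ)) − Φ((−c − √ρ·u)/√(1−ρ))]^k du, by numerical integration:

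| ρ | three true nulls | two true nulls |
|---|---|---|
| 0 | 14.3% | 9.75% |
| 0.5 | 12.5% | 9.1% |
| 0.8 | 9.8% | 7.8% |
| 0.9 | 8.4% | 7.0% |

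**The design as written.** A simulation stopped at the interim on primary success (boundary 0.014), otherwise went to the final analysis, and tested the three secondaries at 0.05 at whichever look was reported. It assumed 495 evaluable subjects (550 × 0.9), a primary effect of either zero or the planned −2.0 days with SD 6.8, and a common correlation among all four statistics. The chance of at least one false secondary result was 9.6% to 14.3% for ρ from 0.8 to 0, whether or not the primary effect was real. This agrees with the one-look table.

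**Would conditioning on the primary be enough?** Allowing secondary claims only after primary success, still at 0.05 each, gives 0.7% (ρ = 0) to 3.7% (ρ = 0.8) when the primary null is true. At the planned primary effect it gives 12.9% (ρ = 0) to 5.9% (ρ = 0.8). An order or an adjustment is needed as well.

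**Power of the first test in a sequence.** Protocol 1.1 gives 50% responder rates of 39.9% (70 mg) and 23.5% (placebo) in the global chronic migraine study. The mean rate is 0.317. Power ≈ Φ{[0.164 − z·√(2 × 0.317 × 0.683/n)] / √[(0.399 × 0.601 + 0.235 × 0.765)/n]}, a two-proportion approximation to the planned CMH test.

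- Final, 0.046 (z = 1.995): n = 247 per arm (495/2) gives 97%. The plan counts missing responders as non-responders in the FAS, so n = 275 is nearer the planned denominator and gives 98.5%.
- Interim stop, 0.014 (z = 2.457): n = 192 per arm (385/2) gives 84%; n = 173 (after 10% dropout) gives 80%.

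**The case against.** The strongest reply is that this is a disclosed choice. Both documents call the secondary intervals and p-values nominal, a null hypothesis and alpha spending are stated only for the primary, and no passage promises a confirmatory or label claim from the secondaries. That stands, and it keeps the point from being an error. It does not close it, because the protocol also says that the endpoints will be tested at a named significance level and never says that the results are descriptive only.

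A reader might infer that the secondaries get two chances at 0.05, one per look, and that the family error is larger still. The documents do not support this. If the interim is not positive, its results stay with the DMC (Protocol 12.7). If it is positive, the interim becomes the reporting look, and later data go into an addendum presented mainly as summary statistics (SAP 2.1). Inference on the secondaries is reported at one look.

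It is also fair to say that the 14.3% is conditional on all three nulls being true. The cited responder rates suggest that at least one may not be, and the two-null column of the table is then the relevant one. Finally, a secondary claim after a failed primary is possible on paper, but the documents describe no such use: submission from the interim is tied to a positive read-out.

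**Conclusion.** The point holds as a cheap improvement. The rule for the secondaries has no order, no adjustment and no dependence on the primary. The chance of at least one false result at the reporting look is 14.3% under independence and 8.4% at correlation 0.9 if all three nulls are true, or about 7% to 10% if two are. These figures rest on assumed correlations and on those null configurations.

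A reader might take this as a weakness of the primary test. It is not: the primary type I error is controlled by its own boundaries and is untouched. What follows is narrower. With tests that are only nominal, the trial cannot offer error-controlled secondary claims in its submission, although it analyses all three endpoints at the look that may be submitted.

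**What to change.** Before unblinding, add to SAP 2.6.2, and align the sentence in Protocol 12.5.1 and the summary:

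1. Secondaries are tested formally only if the primary crosses its boundary at the look being reported.
2. They are tested in a pre-specified fixed order, for example 50% responder rate, then acute headache medication days, then mMIDAS.
3. Each is tested at the O'Brien-Fleming level for that look: 0.014 at 70% information, 0.046 at the final analysis, or the levels recalculated from the actual information.
4. Nominal p-values and intervals for all endpoints remain as descriptive output.

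If no secondary claims are wanted, one sentence calling these tests descriptive, with the 0.05 level removed, would also settle the matter.

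No patients, visits or data are added. The rule sits in the protocol, so a written amendment is needed (Protocol 14.1) as well as a SAP change. The statistical cost is that a miss blocks formal claims lower in the sequence. With the cited responder rates the first test has about 97% to 98.5% power at the final analysis but only about 80% to 84% at an interim stop, where there is no second chance. Power for the other two endpoints cannot be worked out, because the documents give no effect sizes for them; the sponsor should weigh this when fixing the order.

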#### **12.5.2 Safety endpoints**

Safety analyses for the double-blind treatment period and the safety follow-up period will be conducted on SAF set. Safety data will be presented by actual treatments. Safety variables for the double-blind treatment and safety follow-up period include:

- Adverse events
- Clinical laboratory values, vital signs, and ECG
- Anti-AMG 334 antibodies

Safety data for the open-label treatment period will be conducted on OAS. [REDACTED]

[REDACTED]

[REDACTED]

### **Adverse events**

The Medical Dictionary for Regulatory Activities will be used to code all adverse events (AEs). A treatment-emergent adverse events (TEAE) is defined as any adverse event that develops after initiation of study treatment until the end of the last study visit or any event already present that worsens following exposure to the study treatment until the end of the last study visit. Subject incidence rates of TEAEs will be tabulated by SOC and PT by treatment group, separately for the double-blind period [REDACTED]. Tables of TEAE by maximum toxicity grade, fatal AEs, serious AEs, AEs leading to withdrawal from investigational drug, treatment-related AEs, and serious treatment-related AEs will also be presented in a similar format as TEAE. Additionally, a listing of subject with TEAE will be presented. The TEAEs identified as potential risk will be summarized separately.

### **Laboratory data**

The mean and change from baseline values of laboratory data will be summarized over time. Shift tables of the most extreme post-baseline value from baseline will be tabulated.

### **Vital signs**

Vital sign measurements and their change from baseline will be summarized with descriptive statistics (mean, median, standard deviation, min, max) by visit. The number and percentage of subjects with clinical notable vital signs will be presented.

### **ECG evaluations**

ECG intervals will be summarized by presenting summary statistics for changing from baseline values. The incidence rate of clinically notable ECG abnormalities will be summarized.

### **Anti-AMG 334 antibodies**

[figure not shown]
The number and percentage of subjects who develop anti-AMG 334 antibodies (binding and if positive, neutralizing) at any time will be tabulated by treatment group.

[REDACTED]

[REDACTED]

[REDACTED]

[REDACTED]

## 12.7 Interim analyses

To account for potential larger than expected variability during the study, a **blinded** sample size re-estimation is planned after about **50%** (275) subjects finish their treatment or early withdraw. Only the standard deviation of the primary variable, change from baseline in monthly migraine days in the last 4 weeks of the 12-week treatment period based on pooled (blinded) data, will be estimated. The sample size will be increased appropriately if the standard deviation is larger than expected. The blinded sample size re-estimation will be conducted by study team.

An **unblinded interim analysis** for potentially stopping the trial early for efficacy will be implemented when approximately **70%** (385, if no increase of sample size is needed following the blinded IA) of subjects finished the double-blind treatment period or discontinued from the study. The significant level will be adjusted using the alpha spending function with the O'Brien-Fleming boundary. An observed two-sided p-value  $\leq 0.014$  will be required at 70% information. The adjusted significance level based on the actual information included in the interim analysis will be used. If the study proceeds after interim analysis, the hypothesis test will be performed at the end of the double-blind treatment period using the pre-planned final adjusted significance level.

This unblinded analysis will be conducted and reviewed by an independent DMC. Interim results and unblinded data will not be accessible to Novartis personnel who are managing trial operations nor to study investigators and raters. Only DMC members will receive unblinded results. Detailed operating procedures will be specified in a DMC charter, which will define the composition and responsibilities of the DMC members as well as the detailed procedure for handling unblinded data within the DMC and for sharing with Novartis management personnel who is not part of the study team. The interim analysis will focus on the primary efficacy endpoint, but the DMC recommendation on whether to stop the trial or not will be based on the evaluation of totality of efficacy and safety data at interim cut-off. The detailed decision algorithms will be described in the DMC charter.

In case of a positive IA read-out with 70% information, the analysis results will be prepared for regulatory submission. Subjects who are ongoing at the cut-off time of the interim analysis will not be included in the unblinded interim analysis. Their data and all data collected beyond the IA cut-off will be analyzed separately.

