- **Safety follow-up (8 weeks):** in subjects completing the double-blind treatment period, but not entering into the open-label treatment period, a safety follow-up visit will occur 8 weeks after the Week 12 visit (Week 20). Subjects who discontinue study drug during the double-blind treatment period and who do not remain in the study to follow the assessment schedule until the Week 12 FUP visit, will have the safety follow-up visit 12 weeks after the last dose. For subjects discontinuing double-blind treatment and remaining in the study to follow the assessment schedule until the Week 12 FUP visit, the Safety Follow-Up visit should occur on Week 20 even if the last dose was taken at Day 1. The Safety Follow-Up visit is not required in subjects who discontinue or complete the open-label treatment period.
- **Open-label treatment (until launch of erenumab in the country or until June 2021 in Korea):** all subjects completing the double-blind treatment period on study drug are invited to participate. Eligible subjects who consented to participate in this open-label treatment period will receive erenumab until it is launched in the country, or until June 2021 in Korea, in order to ensure continued drug access.

Should a treatment gap exist between the two treatment periods due to a delay of HA/EC approvals or other administrative/logistical reasons, the subject may enter the open-label treatment period at a later time provided he or she still meets the eligibility criteria. During this treatment gap, the subject is allowed to use standard of care.

See the assessment schedule in [Table 8-1](#).

Two interim analyses (IA) are planned for this study:

- A **blinded IA**, after approximately 50% (275) of subjects have completed the double-blind treatment period (including early withdrawals), will be conducted to re-estimate the sample size by providing information on the variance for this trial relative to the planned assumptions to account for potential higher variability in general Asian population.

- An **unblinded IA** will be conducted after 70% (385, if no increase of sample size is needed following the blinded IA) of subjects have completed the double-blind treatment period (including early withdrawals), to determine whether the study will stop early or continue to the final primary analysis (full sample size). Study recruitment will continue until unblinded IA read-out.

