## 12 Data analysis and statistical methods

The primary analysis will include double-blind treatment data as well as safety follow-up data available at the time of the cut-off. Ongoing subjects at the time of the cut-off will not be included.

Additional analysis will be performed at the end of the study, when all subjects have completed their respective last visit (LPLV).

Interim analyses will be performed at planned time points with details defined in [Section 12.7](#).

Any data analysis carried out independently by the investigator should be submitted to Novartis before publication or presentation.

As this study is a China-centric study, the primary and interim analyses (only if early stop for efficacy) will be repeated for Chinese population for primary endpoint, secondary endpoints, and important safety evaluations (i.e. adverse events). The consistency of treatment effect of primary endpoint in Chinese population will be evaluated accordingly.

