### 12.1 Analysis sets

The following analysis sets are defined for the double-blind treatment period:

The **Full Analysis Set (FAS)** includes all subjects who were randomized in the study. Subjects will be analyzed according to their randomized treatment, regardless of the treatment received. Tabulations of demographic and baseline characteristics, disposition, important protocol deviations (IPDs), and efficacy analyses will utilize this analysis set.

The **Safety analysis set (SAF)** will consist of all randomized subjects who received at least one dose of investigational product. In SAF, subjects will be analyzed based on actual treatment received. Safety analyses will be performed based on SAF.

The following analysis set is defined for the open-label treatment period:

The **Open-label treatment analysis set (OAS)** will consist of all subjects who consented to enter into the open-label treatment period and who have taken at least one dose of erenumab during the open-label treatment period. This analysis set will be used when summarizing data collected during the open-label treatment period.

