2.1 Data analysis general information

Data from the study will be analyzed based on the study phase as defined in Table 2-1. The full scope of data analysis defined in this document is pertinent to both DB period (including safety follow-up), and OLE period. The sub-scope of data analysis for the unblinded interim readout is defined in section 2.12.

Table 2-1 Study Phases for data analysis

Study Phase	Start Time Point	End Time Point
DB Period (including Safety follow-up)	Study Day 1 (after the 1st DB IP Dose)	For subject who won't join in OLE: end of study date; For subject who join in OLE: the End of Treatment visit in DB period (the last visit scheduled in DB Period)
OLE Period (applicable for subjects continuing OLE treatment)	The End of Treatment Visit in DB Period + 1	For subject who join in OLE: end of study date

*In general, if the End of Treatment visit date of DB period and the 1st OLE IP injection are on the same day, then the AE or CM which occurs on that day will be considered to belong to DB

period. [REDACTED]

In the case of a positive unblinded IA read-out (success), an interim CSR based on the 70% subjects (DB period completers or early withdrawers up to the unblinded IA cutoff) who are included in the unblinded IA analysis will be generated. The primary analysis will be performed for DB period. Ongoing DB period subjects at the time of unblinded IA cutoff will not be included in this interim CSR. Their data will be reported in an addendum for the interim CSR, when all subjects completed their last visit in DB period. In this interim CSR addendum, those ongoing subjects together with the 70% subjects who have been included in the interim CSR, will be analyzed again and data will be mainly presented by summary statistics. The interim CSR and its addendum will be prepared for regulatory submission.

In case the trial needs to continue enrollment to full sample size as all enrolled subjects have completed DB period, the primary database lock will then be performed. One interim CSR based on all data from DB period and safety follow up collected up to the cutoff timepoint for the primary lock will be prepared for regulatory submission.

At the end of OLE period, a final CSR for data from OLE will be prepared supplementally.

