2.12 Interim analysis

2.12.1 Blinded Sample Size Re-estimation

To account for potential larger than expected variability during the trial, a blinded interim assessment is planned after about 50% of subjects finish 12 weeks' DB treatment or early withdraw. Only the standard deviation of the primary variable, change from baseline in monthly migraine days in the last 4 weeks, based on pooled (blinded) data from all subjects who had the opportunity to complete the week 12 assessment in the trial, will be estimated. The sample size will be increased appropriately if the standard deviation is larger than 6.8.

The type I error of the primary analysis will be maintained, as the treatment assignment will remain blinded and there is no intention to stop the study early due to efficacy.

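### The unblinded interim set is defined by disposition at cut-off, not by time since randomisation, so it modestly over-represents early withdrawers

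*Protocol*

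**What the plan says.** Protocol 12.7 triggers the unblinded analysis when approximately 70% (385) "of subjects finished the double-blind treatment period or discontinued from the study". It then states: "Subjects who are ongoing at the cut-off time of the interim analysis will not be included in the unblinded interim analysis". Protocol 12 applies the same rule to the primary analysis: "Ongoing subjects at the time of the cut-off will not be included". SAP 2.1 agrees. After a positive read-out it plans "an interim CSR based on the 70% subjects (DB period completers or early withdrawers up to the unblinded IA cutoff) who are included" in the analysis, and it reports the subjects still on treatment later, in an addendum made up mainly of summary statistics.

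Protocol 3 keeps enrolment open: "Study recruitment will continue until unblinded IA read-out". The full analysis set, on which efficacy is to be analysed, "includes all subjects who were randomized in the study" (Protocol 12.1). No interim restriction of that set is defined. SAP 2.12.2 lists the interim outputs but does not name a cohort.

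The blinded re-estimation in SAP 2.12.1 has a similar trigger (finished or withdrew early) but a different analysis set: "pooled (blinded) data from all subjects who had the opportunity to complete the week 12 assessment in the trial".

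**The concern.** Take two subjects randomised three weeks before cut-off. The one who withdraws is in the interim set. The one who stays on treatment is not. For subjects randomised in the last 12 weeks, membership therefore depends on something that happens after randomisation.

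At the full sample size the rule is harmless, because nobody is then still on treatment. It bites only at the unblinded look, which spends alpha and can stop the trial. If the trial stops there, this set supports the primary analysis and the regulatory submission, and under the plan's own assumptions stopping is the likelier outcome.

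The extra withdrawers lack Week 12 data. They count as non-responders (SAP 2.6.3), receive baseline-carried-forward or imputed values in the sensitivity analyses (SAP 5.1.5.3), and appear in the disposition and safety tables.

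**Working it through.** **Inputs from the documents.** Total 550; interim at 70%; dropout d = 10%; difference 2.0 days; SD 6.8; 1:1 allocation; interim two-sided p ≤ 0.014, final ≤ 0.046 (Protocol 12.7 and 12.8.1). Double-blind period 12 weeks.

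**Assumptions, not in the documents.** Accrual r = 4 to 14 per week; timing of withdrawal; dropout by arm; how much worse withdrawers do.

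**1. The plan's figures.** For 90% power, n per arm = 2 × 6.8² × (1.960 + 1.282)² / 2.0² = 243, so 486 in all, and 486 / 0.9 = 540, close to 550. With 275 × 0.9 = 247.5 evaluable per arm, power is 0.905 at alpha 0.05 and 0.899 at 0.046. The interim count is 0.70 × 550 = 385. The plan's sample size is reproduced.

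**2. Chance that the interim set becomes the confirmatory one.** Evaluable per arm = 385 × 0.9 / 2 = 173. SE = 6.8 × √(2/173) = 0.73. Expected z = 2.0 / 0.73 = 2.74, against a critical value of 2.46 for p = 0.014. Probability = Φ(2.74 − 2.46) = 0.61.

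**3. Withdrawers in the interim set.** In the 12 weeks before cut-off 12r subjects are randomised. A fraction d of them will withdraw, and a fraction f of those have done so by cut-off. If withdrawal times are uniform over 12 weeks, f = 0.5. If all fall in the first 4 weeks, f = (4 × 0.5 + 8)/12 = 10/12.

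- Recent withdrawers: x = 12 × r × d × f
- Older subjects in the set: N0 = 385 − x
- Withdrawn share = (N0 × d + x) / 385
- Ongoing subjects left out = 12r − x

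| r per week | f | x | N0 | Withdrawn share | Left out | Randomised by cut-off |
|---|---|---|---|---|---|---|
| 4 | 0.5 | 2.4 | 382.6 | 40.7/385 = 10.6% | 45.6 | 430.6 |
| 14 | 0.5 | 8.4 | 376.6 | 46.1/385 = 12.0% | 159.6 | 544.6 |
| 14 | 10/12 | 14.0 | 371.0 | 51.1/385 = 13.3% | 154.0 | 539.0 |

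Simulated accrual and withdrawal give the same picture for withdrawal spread over 12 weeks: 10.5% to 12.1%, with 2 to 9 recent withdrawers. The third row shows that early clustering would add a little more. A set based on time since randomisation has an expected share of 10% (38.5 of 385).

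**4. Effect on the primary test.** In a simulation of a repeated-measures analysis (2,000 trials per setting, dropout dependent on observed or on unobserved values, the same mechanism in both arms), rejection under the null at the 0.0148 level was 1.05% to 1.45% with the planned set and 1.15% to 1.65% with the set based on time since randomisation. At a true −2.0 days the mean estimates differed by at most about 0.013 days, and interim power by about 1 point.

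**5. Effect with unequal dropout.** Suppose withdrawers do g days worse. The shift in the difference is g × [(active share − active dropout) − (placebo share − placebo dropout)]. Take 15% dropout on placebo and 5% on active.

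- r = 5, f = 0.5, g = 2: shares 16.0% and 5.4%; shift = 2 × (0.0037 − 0.0099) = −0.01 days.
- r = 14, f = 10/12, g = 6: shares 19.6% and 6.8%; shift = 6 × (0.0176 − 0.0455) = −0.17 days.

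A negative shift favours erenumab. The formula gives each withdrawer full weight. The observed-data mixed model gives less weight to a subject without Week 12 data, so these figures lean high for the primary analysis and fit an analysis that fills in withdrawers' values better.

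**The case against.** The strongest reply is that the rule is prespecified, stated the same way in both documents, and almost without effect on the primary test. That largely stands. There is no contradiction between Protocol and SAP to reconcile. The primary model uses observed monthly data, and an interval with fewer than 14 diary days is set to missing (SAP 5.1.5.1), so very early withdrawers add nothing to it.

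The size may also be smaller than shown. Protocol 4.5 cites about 95% retention at 3 months on active treatment. At 5% withdrawal, x is only 12 × 4 × 0.05 × 0.5 = 1.2 to 12 × 14 × 0.05 × 0.5 = 4.2 subjects. Protocol 9.1.1 does not treat a subject who stops treatment as withdrawn from the study, and such subjects may stay for follow-up visits. If they count as ongoing, fewer enter early. The documents do not settle which it is, and that is itself a reason to define the set by randomisation date.

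There are mitigations. The SAP 2.1 addendum analyses the omitted subjects together with the 70%. SAP 2.5.4 and 5.1.5.3 provide multiple imputation, baseline carried forward and a review of missingness by arm. But the addendum is mainly descriptive, and the missing-data methods act on whoever is in the set. Neither undoes the selection.

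A reader might infer three stronger things. One is that the set is selected on migraine days. It is not: selection is on disposition, which relates to efficacy only if withdrawal does. Another is that the interim test is anti-conservative; the simulation shows no inflation. The third is that faster accrual makes the problem much larger. At 15 per week about 170 subjects would be left out, and 385 + 170 = 555 exceeds the planned 550. Protocol 3 also allows the interim to be cancelled if recruitment is exceptionally fast.

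**Conclusion.** The point holds as a matter of definition and is small in effect. With 10% withdrawal spread over 12 weeks and accrual of 4 to 14 per week, withdrawers make up about 10.5% to 12.1% of the interim set instead of 10%, and about 45 to 160 contemporaries still on treatment are excluded.

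With equal dropout by arm there is no type I error inflation and essentially no shift in the primary estimate. With unequal dropout, the non-responder-imputed responder rate, the baseline-carried-forward analysis and the disposition figures are distorted, and the primary estimate to a small degree: 0.01 to 0.17 days against a planned 2.0, under an assumed 15% versus 5% dropout that nothing in the documents supports or excludes.

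This does not show that the interim analysis is invalid. It is worth correcting because the set has about a 61% chance of becoming the confirmatory dataset, and because the SAP already has better wording for the look that spends no alpha.

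**What to change.** In Protocol 12.7 and SAP 2.1 and 2.12.2, define the unblinded interim set as all subjects randomised at least 12 weeks, plus a stated visit window, before cut-off, whatever their status. This carries the SAP 2.12.1 principle over to the unblinded look. Set the cut-off at the date when 385 subjects meet that condition. The question of whether someone who stops treatment but stays in follow-up is withdrawn or ongoing then no longer affects membership.

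The cost is about one sentence in each place and a slightly later cut-off. Waiting for x more subjects at r per week takes x/r = 12 × 0.10 × 0.5 = 0.6 weeks, about 4 days whatever the accrual rate, plus the visit window. If all withdrawals fell in the first 4 weeks it would be 12 × 0.10 × 10/12 = 1 week.
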